2.8.2.2.4. Other Secondary Endpoints

Binary secondary efficacy endpoints will be summarized with exact 95% CI by dose for the FAS population. Non-responder imputation will be used to handle missing data.

For each of the continuous secondary efficacy endpoints, 2 analyses will be performed by dose for the FAS population:

1. A time-weighted average analysis will be performed. The time-weighted average of the change from baseline is defined as the area-under-the-curve (AUC) of the change from baseline divided by the observation time over the study period. The AUC of the change from baseline is calculated by the trapezoidal rule using all observed change from baseline data. Summary statistics and 95% CI for the mean time-weighted average will be provided. One-sample t-test will also be performed.

2. A repeated measures model with the baseline value of the endpoint and time as fixed effects will be used to estimate the mean change from baseline over time. Time will be defined as a categorical variable in weeks according to the scheduled visits (Section 2.6). A generalized estimating equation approach with an autoregression (AR(1)) working correlation structure will initially be used to estimate the model parameters. If estimation of this model fails due to any reason, alternative model specifications (e.g., linear, quadratic, or log-scale time trends) will be considered by examination of the data. The least squares mean change from baseline will be estimated with 95% CI for each time point.

In addition, efficacy laboratory values of platelet count, LDH, creatinine, hemoglobin and haptoglobin will be plotted over time for the HSCT-TMA patients.

2.8.2.2.5. Additional Analysis of Secondary Efficacy Endpoints

The analyses of the secondary efficacy endpoints specified in the previous sections (Section 2.8.2.2.1, 2.8.2.2.2, and Section 2.8.2.2.4) will be performed separately for the responders and non-responders for the FAS population.

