2. STATISTICAL METHODS

2.1. Study Endpoints

The co-primary endpoints are:

- Safety as assessed by adverse events (AE)s, vital signs, electrocardiograms (ECG)s, and clinical laboratory tests (includes patients with HSCT-TMA, aHUS, and TTP)
- For HSCT-TMA patients, response to OMS721 treatment. A responder is defined as a patient with HSCT-TMA who demonstrates improvement in laboratory TMA markers (platelet count and LDH) and clinical benefit (either improvement in organ function or reduction in transfusion burden). The specific criteria are defined as follows:
 - Improvement in laboratory TMA markers:
 - Platelet count:
 - For patients with baseline platelet count $\leq 20,000/\mu\text{L}$:
 - Tripling of baseline platelet count
and
 - Post-baseline platelet count $> 30,000/\mu\text{L}$
and
 - No platelet transfusions 2 days before and on the day of the platelet count collection
 - For patients with baseline platelet count $> 20,000/\mu\text{L}$
 - Increase in platelet count $\geq 50\%$
and
 - Post-baseline platelet count $> 75,000/\mu\text{L}$
and
 - No platelet transfusions 2 days before and on the day of the platelet count collection
 - and
 - LDH:
 - LDH < 1.5 x upper limit of normal (ULN)

and

- Improvement in clinical status:
 - Improvement in organ function as evidenced by any of the following:
 - Improvement in renal function:
 - Reduction of creatinine > 40%
 - or
 - Creatinine < ULN and reduction of creatinine > 20%
 - or
 - Discontinuation of renal replacement therapy (RRT),
 - or**
 - Improvement in pulmonary function:
 - Extubation and discontinuation of ventilator support
 - or
 - Discontinuation of non-invasive mechanical ventilation (continuous positive pressure ventilation)
 - or**
 - Improvement in neurological function:
 - Improvement in reversible neurological conditions (e.g., cessation of seizures)
 - or
 - Stabilization of irreversible neurological conditions (e.g., stability of neurological deficits following stroke without further deterioration or subsequent strokes)
 - or**
 - Improvement in gastrointestinal function (gastrointestinal HSCT-TMA will require diagnosis by tissue biopsy):
 - Improvement measured by improvement in the gastrointestinal measures in the Mount Sinai Acute GVHD International Consortium (MAGIC) criteria
 - or**

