2.8.2. Efficacy Analyses

2.8.2.1. Primary Efficacy Endpoint

A patient is a responder if this patient meets the responder criteria (Section 2.1) at any time post-baseline during the study. If a patient is not evaluable for a response criterion due to confounding factors, the non-evaluable response criterion will not be included in the determination of responder. Evaluability of each response criterion will be determined by a clinical review of relevant data and will be documented in the clinical study report. For example, potential confounding factors include graft failure for platelet count or transfusions, and nephrotoxic medications for renal function. Furthermore, laboratory values collected from both the local laboratories and the central laboratories will be used to determine response status.

Analysis of the primary efficacy endpoint will use a non-responder imputation to impute missing or incomplete data to evaluate response. The number and percent of responders will be summarized with exact 95% CI (Clopper-Pearson) by dose and total for the FAS and PAS

populations. If the lower bound of the exact 95% CI is greater than 15%, there is sufficient evidence to demonstrate efficacy of narsoplimab in the target patient population. Each criteria of the response will be listed for each patient.

Sensitivity analyses will include:

1. Subgroup analyses for the following subgroups will be performed for the FAS population:
 - Age (< 65 , ≥ 65 years)
 - Gender (Male or Female)
 - Graft-versus-host disease (GVHD) (Yes or No)
 - Significant infection (Yes or No)
 - Graft failure or non-engraftment (Yes or No)
 - Female-to-male transplant (Yes or No)
 - Multiple organ TMA involvement (Yes or No)
 - Mismatched donor (Yes or No)
 - Baseline platelet counts ($< 20,000$ or $\geq 20,000$ platelets/ μL)
 - Renal dysfunction at baseline (Creatinine $> \text{ULN}$ or spot urine protein $\geq 2+$ or > 30 mg/dL; Yes or No)
 - Any transfusions within the 2 weeks prior to or on the first OMS721 dose date (Yes or No)
2. A completer analysis will be performed using the patients with non-missing responses only. Exact 95% CI for the completer response rate will be provided for the FAS population by dose.
3. Two alternative definitions of response will be analyzed:

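### The SAP reruns the one-sample t-test within responders and non-responders; for platelets this is circular, because response is defined by a platelet rise

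*SAP*

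**What the plan says.** SAP 2.8.2.2.5 takes the analyses already specified for 100-day survival, overall survival and the other secondary endpoints and says that they (Section 2.8.2.2.1, "2.8.2.2.2, and Section 2.8.2.2.4) will be performed separately for the responders and non-responders for the FAS population". It gives no purpose, caveat or restriction for the split.

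For the continuous endpoints (platelets, LDH, haptoglobin, hemoglobin, creatinine), SAP 2.8.2.2.4 specifies by dose:
- a time-weighted average change from baseline, for which "Summary statistics and 95% CI for the mean time-weighted average will be provided" and "One-sample t-test will also be performed";
- a repeated measures model with 95% intervals at each time point.

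The transfusion endpoints are handled differently: "Binary secondary efficacy endpoints will be summarized with exact 95% CI by dose for the FAS population".

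SAP 2.1 defines response. The platelet limb depends on baseline. If baseline is above 20,000/µL, the count must rise by at least 50% and exceed 75,000. If baseline is 20,000 or lower, it must triple and exceed 30,000. LDH must be below 1.5 x ULN. One clinical route must also be met, out of renal, pulmonary, neurological or gastrointestinal improvement or freedom from transfusion. SAP 2.8.2.1 counts a patient who meets the criteria "at any time post-baseline during the study", using local and central laboratory values, and drops criteria judged non-evaluable.

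**The concern.** The two groups are formed after baseline, partly on the variable that is then tested. A patient evaluable on platelets cannot be a responder without a substantial rise, so asking whether the mean platelet change in that group differs from zero mostly restates the classification. Ordinary fluctuation or spontaneous recovery is enough to place a patient in the responder group, and the t-test makes no allowance for that selection. Non-responders are selected the opposite way and can show apparent worsening.

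What is at stake is interpretation. Protocol 12.5.1 presents the secondary measures as population-level support for the individual responses. The results go into an interim report intended for a regulatory submission (SAP 2.8.5). A small p-value for platelets within responders could be read there as independent support for the response rate, which it is not.

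**Working it through.** **Plan's own figures.** The plan gives no operating characteristics for this split. Its sample-size figures do reproduce. With 28 patients the exact 95% interval is 12.34 percentage points wide at 0/28 and 38.71 at 14/28, and 14/28 gives 30.65% to 69.35%. SAP Table 1 has 2 + 22 = 24 HSCT-TMA patients at 4.0 mg/kg and 4 at 370 mg. A split by dose and response therefore leaves at most 4 patients in any 370 mg group.

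**Step 1: what the definition forces.** Let b be baseline in thousands per µL.
- b > 20: the qualifying count must be at least 1.5b and above 75, so the rise is at least max(1.5b, 75) - b. This is smallest at b = 50: 75 - 50 = 25.
- b ≤ 20: the qualifying count must be at least 3b and above 30, so the rise is at least max(3b, 30) - b. This is smallest at b = 10: 30 - 10 = 20.

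Every responder evaluable on platelets has therefore, on at least one date, been more than 20,000/µL above baseline. Because counts on neighbouring days are correlated, part of that excess carries into the time-weighted average.

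**Step 2: size under no effect.** Simulation, N = 28, 3,000 trials per scenario, visits on Days 1, 8, 15, 22, 29, 36, 50 and 92, and mean change set to zero in the full population. The SAP 2.1 platelet and LDH limbs and the clinical routes were applied. With c_j the change from baseline at day d_j:

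TWA = Σ [(c_j + c_(j-1))/2 × (d_j - d_(j-1))] / (92 - 1), then t = mean(TWA) / (s/√n), two-sided 5%.

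Assumptions, none from the documents, for the first five rows: median platelets 50,000/µL, LDH 1.6 x ULN, creatinine 1.8 x ULN, within-patient log SD 0.3, weekly autocorrelation 0.6, transfusion freedom 40%, other organ routes 15%. The last row uses platelets 60,000, LDH 1.3 x ULN and transfusion freedom 60%. Slope SD is the spread of patients' spontaneous courses on the log scale. Correlation is between markers. Groups of fewer than 3 were not tested.

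| Slope SD / correlation | Mean responders | Platelets: all / responders / non-responders | LDH: responders | Creatinine: responders |
|---|---|---|---|---|
| 0 / 0 | 2.2 | 4.7% / 35.7% / 7.2% | 3.9% | 4.0% |
| 0.5 / 0 | 3.2 | 5.3% / 40.1% / 17.5% | 8.0% | 6.6% |
| 0.5 / 0.5 | 4.3 | 5.4% / 54.4% / 30.2% | 20.6% | 24.8% |
| 0.8 / 0.5 | 5.2 | 7.6% / 56.0% / 64.5% | 46.2% | 43.5% |
| 0.8 / 0.8 | 6.0 | 7.1% / 63.3% / 84.6% | 66.4% | 66.1% |
| 0.8 / 0.5 (last row settings) | 6.5 | 6.3% / 60.1% / 78.1% | 45.8% | 42.0% |

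In these rows the mean platelet shift in responders was +21,000 to +63,000/µL, with none in the full population. Over a wider set of scenarios (within-patient log SD 0.22-0.5, weekly autocorrelation 0.3-0.8) responder rejection for platelets was 26-63%, against 4.2-7.6% unsplit across the three markers.

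**Step 3: other set-ups.** A simulation with 24 patients and the platelet limb only, judging response on daily values but averaging over central visits, found significant improvement in responders in 20-57% of null trials, against 2-4% unsplit (nominal one-sided 2.5%). It varied log SD over 0.3-0.5 and daily autocorrelation over 0.90-0.97. A further null simulation gave 18-72%, against 4-6% unsplit.

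**Step 4: the other endpoints.** For LDH and creatinine, responder rejection stays at or below 8% unless spontaneous courses vary and are correlated between markers; it is then 21-66%. In the table rows, transfusion freedom was 43-58% in responders when 40% overall, and 65% when 60% overall: a gap of 3 to 18 percentage points. Hemoglobin and haptoglobin were not simulated.

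**The case against.** The strongest defence is that little depends on this split. SAP 3.1 calls all summaries descriptive. The only success rule is the lower confidence bound for the response rate (SAP 2.8.2.1). The unsplit analyses stay in place, and the section is headed as an additional analysis. An interval can also fairly describe the average among patients classed as responders. All of this stands, and it limits the importance of the point. It does not rescue the t-test, which is an inference against zero rather than a description.

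A reader might go further and infer that every rerun analysis is invalid by construction. The documents do not support that:
- The LDH limb is a level, not a fall. Raised LDH is one of three listed signs of hemolysis at entry, joined by or (Protocol 8.1), so a patient may meet the limb at baseline.
- Creatinine and freedom from transfusion are two of several alternative routes, so a responder may have used neither.
- Non-evaluable criteria are dropped, so some responders may not have been selected on platelets at all.
- Response draws on local and central values at any time, whereas the change endpoints use central values averaged over time, which weakens the link.
- Transfusion endpoints get exact intervals, not t-tests.

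A reader might also infer that the responder tables are bound to show significance with an inactive drug. The simulations do not show that: in many null trials the responder platelet test does not reject. Nor does any passage say that the split is intended to corroborate the primary endpoint.

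**Conclusion.** The point holds for platelets, as a matter of definition, among patients evaluable on that criterion. The within-group t-test does not measure a drug effect: under no effect it rejects in roughly 20-70% of simulated trials in responders, against about 5% unsplit. The direction follows from the response rule. The size is illustrative and rests on assumed variability, autocorrelation, disease course and how many response limbs are modelled. The simulated responder groups are also small.

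For LDH, creatinine, transfusion freedom, hemoglobin and haptoglobin, bias is possible because all are examined in groups formed on a post-baseline outcome. Its size depends on the disease course and may be small. The primary analysis, the 15% rule and the full-population secondary analyses are unaffected. The same SAP sentence also splits survival by response; that raises a separate timing question, not assessed here.

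**What to change.** In SAP 2.8.2.2.5:
1. Remove the one-sample t-test for all continuous endpoints. Keeping it for hemoglobin and haptoglobin would be inconsistent, since they are examined in the same post-baseline groups.
2. Present laboratory and transfusion results by response status as descriptive summaries or plots only.
3. State that the groups are formed on post-baseline values of these variables, so within-group changes and between-group differences are not evidence of a drug effect.

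This takes a few sentences and fewer tables. Protocol 13.2.5.2 does not mention the split, so no analysis described there changes, and no data collection is affected. The downside is that a favourable-looking p-value disappears from the responder tables.

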 - Freedom from transfusion (no transfusions for at least 4 weeks from the last transfusion except for patients who died within 4 weeks of the last transfusion, only evaluated in patients who received transfusions within the 2 weeks prior to or on the first OMS721 dose date).

The secondary endpoints of this study are to evaluate the following in patients with HSCT-TMA treated with OMS721:

- Duration of response defined as the number of days from the first response date to the first relapse date
- 100-day survival, from the date of TMA diagnosis
- Overall survival, from the date of TMA diagnosis
- Freedom from platelet transfusion defined as no platelet transfusions for at least 4 weeks following the last platelet transfusion except for patients who died within 4 weeks of the last platelet transfusion (only evaluated in patients who had platelet transfusions in the 2 weeks prior to or on the first OMS721 dose date)
- Freedom from RBC transfusion defined as no RBC transfusions for at least 4 weeks following the last RBC transfusion except for patients who died within 4 weeks of the last RBC transfusion (only evaluated in patients who had RBC transfusions in the 2 weeks prior to or on the first OMS721 dose date)
- Change from baseline in platelet count (post-baseline platelet counts without platelet transfusions 2 days before and on the day of the platelet count collection will be used) over time using central laboratory values
- Change from baseline in LDH over time using central laboratory values
- Change from baseline in haptoglobin over time using central laboratory values
- Change from baseline in Hgb (post-baseline Hgb without RBC and whole blood transfusions 6 days before and on the day of the Hgb collection will be used) over time using central laboratory values
- Change from baseline in creatinine over time using central laboratory values

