2.8.2.2. Secondary Efficacy Endpoints

2.8.2.2.1. 100-day Survival

The 100-day survival status will be determined as a binary variable. A patient achieves a 100-day survival if the overall survival from the date of HSCT-TMA diagnosis of the patient is greater

than or equal to 100 days. If the 100-day survival status of a patient is unknown (i.e., censored before 100 days), this patient will be considered to have died prior to 100 days. The 100-day survival rate will be estimated with exact 95% CI by dose for the FAS population.

In addition, cumulative incidence at 100 days for each of the pre-specified cause of death (GVHD, graft failure, infections, progression of underlying disease, HSCT-TMA and other) will be estimated by a competing risks analysis (Section 2.8.2.2.2).

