2.8.2.2.2. Overall Survival

Overall survival will be calculated from the date of HSCT-TMA diagnosis. For the patients who are alive, their overall survival will be censored at the last known date of alive in the database. The method for handling a partially missing date of death is presented in Section 2.7.

Overall survival will be analyzed using Kaplan-Meier method by dose for the FAS population. Median overall survival and its 95% CI will be estimated by dose.

In addition, a competing risks analysis for overall survival will be performed. The cumulative incidence function of each pre-specified causes of death (GVHD, graft failure, infections, progression of underlying disease, HSCT-TMA, and others) will be estimated by nonparametric maximum likelihood method. The estimated cumulative incidence functions and their 95% CI will be displayed graphically.

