2.8.2.2.3. Duration of Response

The duration of response will be estimated for the FAS population. Duration of response is defined as the number of days from the first response date to the first relapse date (first relapse date – first response date + 1). The first response date is the first date of platelet count and LDH that a response is achieved. Relapse is defined as having a platelet count greater than 50% decrease from the maximum platelet count and a LDH greater than 1.5 times the upper limit of normal. Relapse will be evaluated using the platelet count and the LDH collected within 1 week. Duration of response will be censored at the last platelet or LDH collection date if relapse does not occur during the study. Kaplan-Meier analysis of the duration of response will be performed for the patients who achieve a response by dose for the FAS population. Median duration of response will be presented with 95% CI.

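### Splitting 100-day and overall survival by ever-responder status favours responders even if response has no bearing on survival

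*SAP*

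**What the plan says.** SAP 2.8.2.2.5 takes the analyses of 100-day survival (2.8.2.2.1), overall survival (2.8.2.2.2) and the other secondary endpoints (2.8.2.2.4) and states that they "will be performed separately for the responders and non-responders for the FAS population". Duration of response is not in the split.

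Four other rules decide how the split behaves:

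- **Who is a responder.** SAP 2.8.2.1: "A patient is a responder if this patient meets the responder criteria (Section 2.1) at any time" after baseline during the study. Missing or incomplete response data count as non-response.
- **Where survival starts.** SAP 2.8.2.2.2: "Overall survival will be calculated from the date of HSCT-TMA diagnosis". The 100-day endpoint has the same origin, which precedes first dose and therefore any response.
- **Unknown 100-day status.** SAP 2.8.2.2.1: "this patient will be considered to have died prior to 100 days".
- **When response is dated.** SAP 2.8.2.2.3: "The first response date is the first date of platelet count and LDH that a response is achieved". This rests on the two laboratory markers and does not show when the clinical part was met.

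Neither document gives a landmark, a time-dependent method, a cut-off date for response or a caution on reading the split. Protocol 13.2.5.2 does not contain the split.

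**The concern.** The groups are defined by something that happens after the survival clock has started. Everyone who ends up a responder was alive from diagnosis to response. Patients who die early have little chance to respond and fall into the other group. One route to clinical benefit makes the waiting time explicit: freedom from transfusion requires "no transfusions for at least 4 weeks from the last transfusion".

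The two missing-data rules can add to this. A patient lost early may count both as a non-responder and as a death before day 100.

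A reader who sets the two sets of tables side by side would tend to conclude that response predicts survival, whether or not it does. Protocol 12.5.1 presents the secondary measures as support for the patient-level responses, and SAP 2.8.5 places the results in an interim report meant for a regulatory submission.

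**Working it through.** **Plan's own figures.** The documents give no figure for the split. The related sample-size figures in SAP 1.3 reproduce: at n = 28 the exact interval widths run from 12.34% to 38.71%, and 14/28 gives 30.65% to 69.35%. They show how little precision two subgroups of 28 patients would have.

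**Direction.** Let T be time to death, R time to response, p the share of patients able to respond, and R independent of T. Then

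P(responder | T = t) = p × F_R(t),

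which cannot fall as t rises. Hence P(T > t | responder) ≥ P(T > t) ≥ P(T > t | non-responder), whatever the distribution of R.

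**Inputs for size**

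- From the documents: about 28 HSCT-TMA patients (SAP 1.3; SAP Table 1 gives 2 + 22 = 24 at 4.0 mg/kg and 4 at 370 mg). One-year survival of 17% (4 of 24 adults on other treatments) is in Protocol 5.1.2.3.
- Assumed: one-year survival from first dose of 17, 40 or 60%, with 80% as a check; p of 50, 60 or 75%; T exponential; R exponential with median 7, 14 or 30/60/90 days, or 28 days plus an exponential time with median 30/60/90; first dose on day 30 after diagnosis, with 14 and 60 as checks.

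**One case by hand** (one-year survival 40%, p = 0.60, median R 30 days, first dose day 30)

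- λ = −ln(0.40)/365 = 0.00251; ρ = ln(2)/30 = 0.02310; u = 100 − 30 = 70 days.
- P(responder) = p × ρ/(ρ + λ) = 0.60 × 0.9020 = 0.541.
- P(T > u) = exp(−λu) = 0.839, the same for everyone.
- P(responder and T > u) = p × [exp(−λu) − λ/(λ + ρ) × exp(−(λ + ρ)u)] = 0.60 × [0.8388 − 0.0980 × 0.1664] = 0.4935.
- 100-day survival: responders 0.4935/0.5412 = 91.2%; non-responders (0.8388 − 0.4935)/(1 − 0.5412) = 75.3%.
- False gap: 15.9 points.

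**All settings.** Simulation used 1,000,000 patients per setting; the closed form above agrees to within 0.2 points. Gaps are in percentage points.

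| Median time to response | First dose day 30, survival 17-60% | First dose day 14-60, survival 17-60% | First dose day 30, survival 80% |
|---|---|---|---|
| 7 days | 2.6-12.3 | 2.4-13.9 | 1.1-2.2 |
| 14 days | 4.8-21.2 | 4.4-21.9 | 2.2-4.3 |
| 30-90 days | 8.2-35.2 | 6.5-37.3 | 3.9-10.4 |
| 28 days added to 30-90 | 13.1-45.7 | 9.0-46.6 | 6.2-12.2 |

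**Samples of 28 with no true link** (20,000 per setting, first dose day 30). The observed gap is zero or reversed in 28.7-46.1%, 14.5-38.3%, 1.8-26.2% and 0.2-13.8% of samples, in the order of the rows.

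**Imputation rules.** If 5-10% of patients were lost before day 100 (assumed), the two rules would add 0.4-3.5, 0.9-6.7, 1.6-13.3 and 2.8-15.4 points.

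**A second set of assumptions** (100-day survival 50-80%, first dose 0 or 21 days after diagnosis, median response time 14-56 days, with or without a 28-day minimum) gave gaps of 11 to 54 points, in favour of responders in all 30 scenarios.

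**Does a landmark remove it?** At Day 50 (49 days after first dose) the null difference in survival 180 days later is at most 0.3 points, which is simulation noise. Expected patients alive: 28 × 0.17^(49/365) = 22.1, and 28 × 0.60^(49/365) = 26.1. Expected landmark responders: 11.0-19.5 at 7 days, 10.1-17.9 at 14 days, 3.5-13.3 at 30-90 days, and 1.7-7.5 with 28 days added.

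**The case against.** **It is only descriptive.** The split is additional, SAP 3.1 calls all summaries descriptive, and no between-group test is named. This stands and limits the weight of the point. It does not remove it: the plan still yields an exact interval and a Kaplan-Meier median for each group, and the obvious use of such tables is to compare them.

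**The size is driven by assumptions.** This also stands. Exclusion criterion 8 bars patients with a life expectancy under 3 months, and early deaths drive the bias. Halving the hazard in the first 90 days, with one-year survival kept at 17-60%, lowers the gaps to 1.3-7.8, 2.6-14.0, 4.4-22.8 and 7.1-30.8 points. The upper ends drop by about a third and the direction is unchanged. The 28-day row is an extreme case, because freedom from transfusion is one of several alternative routes and applies only to patients transfused in the 2 weeks up to first dose.

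**Other remedies exist.** Response as a time-dependent covariate also removes the false difference (death-rate ratio 0.99-1.01 under no association) and keeps the early deaths. But it needs a date of full response for each patient, which the SAP does not define. A landmark needs one yes/no decision at a fixed day. A caveat alone would leave biased tables in the report.

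**Dating is imperfect.** The study is open-label, and Protocol Table 2 does not explicitly ask for the end date of ventilation. Both are fair; hence the rule in the fix to use only data dated by Day 50 and to count what cannot be dated as not met.

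**Conclusion.** The concern holds. As written, the survival split compares groups of which one is guaranteed to have survived to its defining event. If response time is independent of death, the expected difference favours responders whatever the response times are.

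The size cannot be fixed from the documents. With one-year survival of 17-60% and first dose on day 30, the false 100-day gap ranges from about 3 points (fast response) to 35 (slow response), and to 46 if every response takes 28 days longer. It is about 1-12 points at 80% survival. With 28 patients it is a tendency and will not appear in every sample.

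This should be fixed, but it does not threaten the main result: the primary response rate, its 15% criterion and survival in the whole FAS are unaffected.

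**What to change.** For 2.8.2.2.1 and 2.8.2.2.2 only, including their cause-of-death incidence, replace the ever-responder split with one landmark, fixed before the interim database lock:

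- **Day.** Day 50 after first dose, the latest visit day shared by the three HSCT-TMA schedules: Stage 1 (Visit 8), Stage 2 only (F-3) and Stage 3 (T-8).
- **Patients.** Those alive and in follow-up at Day 50, pooled over dose because only 4 patients are in the 370 mg row of SAP Table 1. Survival is timed from the landmark.
- **Response status.** SAP 2.8.2.1 already provides that "Evaluability of each response criterion will be determined by a clinical review of relevant data". The same review decides, from data dated on or before Day 50, whether all criteria had been met by then. It uses dated laboratory, transfusion, renal replacement and ventilation records, not the laboratory-only date of 2.8.2.2.3. A patient who relies on freedom from transfusion must have completed the 4 weeks, so the last transfusion is no later than Day 50 − 28 = Day 22. Any component that cannot be dated by Day 50 counts as not met.
- **Reporting.** Give 100-day survival from diagnosis unsplit, and state that the landmark comparison is descriptive and not causal.

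**Cost.** SAP wording, one added decision in a planned review and a short program. Protocol Table 2 dates each transfusion and renal replacement episode, and records ventilation with dates. Protocol 19.5 collects local laboratory values daily, as available, to at least 12 weeks after diagnosis, which covers Day 50 if first dose is within 84 − 49 = 35 days of diagnosis.

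Some information is lost. Patients who die before Day 50 leave the comparison (about 22 to 26 of 28 remain, before any loss to follow-up), and later responses count as non-response. Table 2 records neurological events by diagnosis date and lists no staging for the gastrointestinal route ("Improvement measured by improvement in the gastrointestinal measures in the Mount Sinai Acute GVHD International Consortium (MAGIC) criteria"), so responses by those routes may count as not met. With perhaps 2 to 19 landmark responders, the result will be imprecise.
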